4. STUDY DESIGN AND ENDPOINTS

4.1 DESCRIPTION OF THE STUDY DESIGN

This is a pilot randomized phase 2 clinical trial to evaluate the efficacy and tolerability of TKI therapy through adaptive (intermittent) versus conventional (continuous) regimen in patients with DTC or MTC. Eligible subjects with DTC or MTC will have measurable disease according to Response Evaluation Criteria in Solid Tumors (RECIST 1.1) and will be randomized 2 to 1 to receive adaptive (intermittent) versus conventional (continuous) therapy when and if the tumor marker drops 50% or more from the baseline level (before initiating TKI treatment) within the first two months of treatment. Randomization will be stratified by cancer types, DTC vs. MTC. Patients in which the tumor marker does not drop by 50% or more within 2 months (“non-responders”) will be kept on conventional therapy and used to compare with the patients who drop their tumor markers by 50% or more as an exploratory analysis.

All patients will start receiving standard of care treatments: Lenvatinib 24 mg daily or Sorafenib 400 mg twice daily with DTC; Cabozantinib 140 mg daily or Vandetanib 300 mg daily with MTC. Doses will be adjusted as needed due to toxicity or drug tolerance in both arms (See section 6.1.8).

- Patients in the conventional therapy regimen (“responders” and non-responders”) will receive continuous (daily) treatment at the indicated dose.

- Patients in the adaptive therapy regimen will receive TKI therapy in cycles: continuous (daily) treatment at the indicated dose until the patients’ tumor marker (thyroglobulin in DTC patients; calcitonin or CEA in MTC patients) drops by $\geq 50\%$ from the level at the time of enrollment (“baseline” level). $\geq 70\%$ of Only tumor markers that meet inclusion criteria at baseline can be used for randomization and adaptive therapy purposes. A new cycle of TKI treatment will begin:

1. When/if the tumor marker increases to $\geq 70\%$ of the “baseline” level.
OR
2. At the discretion of the treating physician, if a patient develops worsening disease-related symptoms with rising tumor marker levels indicating disease progression. In the case of resumption for disease-related symptoms, TKI treatment will continue until the symptoms improve at the discretion of the treating physician and the tumor markers are again $\leq 50\%$ from the level at the time of enrollment.

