6.1.8 DOSE ADJUSTMENTS/MODIFICATIONS/DELAYS

All patients will start receiving standard of care treatment:

- DTC: Lenvatinib 24 mg daily or Sorafenib 400 mg twice daily
- MTC: Cabozantinib 140 mg daily or Vandetanib 300 mg daily.

Dose will be adjusted as needed due to toxicity or drug tolerance in both arms (See below).

- Patients in the conventional therapy regimen (“responders” and non-responders”) will receive continuous (daily) treatment at the indicated dose.

- Patients in the adaptive therapy regimen will receive TKI therapy in cycles: continuous (daily) treatment at the indicated dose until the patients’ tumor marker (thyroglobulin in DTC patients; calcitonin or CEA in MTC patients) drops by $\geq 50\%$ from the level at the time of enrollment (“baseline” level). Only tumor markers that meet inclusion criteria at baseline can be used for randomization and adaptive therapy purposes. A new cycle of TKI treatment will begin:

1. When/if the tumor marker increases to $\geq 70\%$ of the “baseline” level.

OR

2. At the discretion of the treating physician if a patient develops worsening disease-related symptoms with rising tumor marker levels indicating disease progression. In the case of resumption for disease-related symptoms, TKI treatment will continue until the symptoms improve at the discretion of the treating physician and the tumor markers are again $\leq 50\%$ from the level at the time of enrollment.

All study participants will continue to receive treatment until confirmed disease progression, development of unacceptable toxicity, withdrawal of consent, or study termination by investigator.

After disease progression subjects will be followed for survival and may be treated according to standards of care, which includes conventional (continuous) TKI treatment for patients in the adaptive therapy arm.

Held doses will be considered missed and will not be made up so that patients will complete on-study treatment within the anticipated 24 month duration. Treatment may be delayed for toxicity, other palliative treatments (i.e. palliative radiation, palliative surgery, etc.) for a maximum of 4 weeks. Any treatment beyond the 24 months specified herein will be considered off protocol and not subject to the requirements of this protocol.

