10. STATISTICAL CONSIDERATIONS

10.1 STATISTICAL AND ANALYTICAL PLANS

This is a randomized phase II clinical trial with 2:1 randomization to adaptive therapy versus conventional therapy. The primary endpoint is time-to-discontinuation (TTD) of treatment, which is a "survival analysis"-type statistical comparison. We plan to enroll 24 patients on the adaptive therapy and 12 on the conventional therapy arm. Assuming uniform enrollment of patients for 2 years, with a minimum follow-up of 2 years, and a one-sided $\alpha = 0.20$, we will have 82% power to detect a hazard ratio of 0.50, assuming 12 and 24 month median TTD for the conventional and adaptive therapy groups. If the median TTD of the adaptive group is 20 months (HR=0.6), the power is 67%.

We anticipate that 20% of the patients will not have the $\geq 50\%$ drop in tumor markers needed for study randomization arm of the study. Thus, we anticipate recruiting ~45 patients to have 36 patients for randomization.

The ~9 patients enrolled to the trial not candidates for the randomization will be given conventional therapy as standard of care. As an exploratory analysis, and realizing that the sample sizes are small, we will compare their PFS rates with the 12 patients from the randomized portion of the trial who receive conventional therapy using the log-rank test.

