10.2 STATISTICAL HYPOTHESES

We hypothesize that we will prolong time to treatment discontinuation with the adaptive therapy regimen (**experimental group**) compared to the continuous therapy regimen (**control group**). Literature suggests that the median time to discontinuation with standard (continuous) therapy is 12 months. We hypothesize that the median time to discontinuation will increase to 24 months (Hazard ratio 0.50) with the adaptive therapy regimen. The power of the study to detect this difference is 82% for an alpha of 0.20.

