10.3 DESCRIPTION OF STATISTICAL METHODS

10.3.1 ANALYSIS OF THE PRIMARY EFFICACY ENDPOINT(S)

The primary endpoint is the time-to-discontinuation of treatment.

- The measurement endpoint is the status of a patient 12 months following the start of TKI.
- This is a binary metric. 1 = the patients is still receiving TKI at 12 months; 0 = patient is no longer on TKI due to cancer progression and/or toxicity.
- The results will be described as % patients that remain on TKI at 12 months by experimental and control groups.
- The test statistic will a Fisher's Exact test on a two by two contingency table of patient counts based on all four combinations of whether a patient remains or does not remain on TKI (0 or 1) by treatment group (adaptive therapy or continuous therapy)
- We will begin by comparing the historical control patients with the control patients of the trial. If these two groups do not differ (using a Type I error rate of $p > 0.1$) then they shall be combined to provide the patient counts for the Fisher's Exact Test comparison of the control group to the experimental group of the trial.
- If the historical control patients differ from the control patients of the trial (using a Type I error rate of $p < 0.1$) then they will be compared separately to the experimental group using Fisher Exact test's with a Bonferroni adjusted Type I error rate of $p < 0.05$.

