10.4 SAMPLE SIZE

The planned study is a randomized clinical trial, with 2:1 randomization to adaptive therapy versus conventional therapy. The primary endpoint is time-to-discontinuation (TTD) of treatment, which is a “survival analysis”-type statistical comparison. We plan to enroll 24 patients on the adaptive therapy and 12 on the conventional therapy arm. Assuming uniform enrollment of patients for 2 years, with a minimum follow-up of 2 years, and a one-sided $\alpha = 0.20$, we will have 82% power to detect a hazard ratio of 0.50, assuming 12 and 24 month median TTD for the conventional and adaptive therapy groups. If the median TTD of the adaptive group is 20 months (HR=0.6), the power is 67%.

We anticipate that 20% of the patients will not have the $\geq 50\%$ drop in tumor markers needed for study randomization arm of the study. Thus, we anticipate recruiting ~45 patients to have 36 patients for randomization.

Objective time-to-discontinuation criteria are described in Section 4.2.1. Patients may electively withdraw from treatment at any time and will be counted as a discontinuation event. All randomized patients will be included in the primary analysis. A sensitivity analysis will also be conducted, where the patients who choose to withdraw are considered as censored (non-events) at the time of withdrawal.

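### The primary test must absorb an undefined historical control group whenever a weak preliminary test gives p > 0.1, so its error rate depends on patients the plan does not describe

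*Combined protocol and SAP*

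**What the plan says.** Section 10.3.1 reduces the primary endpoint to on or off TKI at 12 months and compares the arms by Fisher's exact test. Before that comes a gate: "We will begin by comparing the historical control patients with the control patients of the trial". If p > 0.1, "then they shall be combined to provide the patient counts" on the control side. If p < 0.1, each control group is compared separately with the adaptive arm, "with a Bonferroni adjusted Type I error rate of" 0.05. The section gives no level or sidedness for the pooled test.

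The rest of the plan describes a purely randomised comparison. Section 10.1: "We plan to enroll 24 patients on the adaptive therapy and 12 on the conventional therapy arm". Sections 10.1 and 10.4 give 82% power for a hazard ratio of 0.50 and 67% for 0.6, at one-sided alpha 0.20, using those 36 patients. Section 10.4 states: "The primary endpoint is time-to-discontinuation (TTD) of treatment". Section 4.1 randomises patients only "when and if the tumor marker drops 50% or more from the baseline level" within two months of starting treatment, and section 10.1 expects 20% of enrolled patients not to reach that point. The nearest thing to historical information is in section 10.2: "Literature suggests that the median time to discontinuation with standard (continuous) therapy is 12 months". That is a planning value, not a description of a control group.

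**The concern.** The pooling is mandatory and it is part of the primary analysis. The available text gives no number, source, period, drug mix or selection rule for the historical patients, so nobody can tell from the plan how the primary test will behave.

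Three things make this more than missing detail.

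- A non-significant result against 12 patients is not evidence that two groups are comparable.
- The randomised controls are a selected group of early marker responders. If the historical patients were not selected in the same way, they plausibly stay on treatment less often, and pooling then favours the adaptive arm.
- If they do better instead, the test becomes conservative and loses power.

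At stake is the protection that randomisation gives to the primary result. The stated alpha of 0.20 and power of 82% do not describe the procedure in section 10.3.1.

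**Working it through.** **1. The plan's own figure.** Inputs from section 10.1: exponential medians of 12 and 24 months, 12 and 24 patients, 24 months' uniform accrual, at least 24 months' follow-up, one-sided alpha 0.20.

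- Event probability = 1 − (e^(−24λ) − e^(−48λ)) / (24λ), with λ = ln 2 / median. This gives 0.865 (control) and 0.639 (adaptive).
- Expected events: 12 × 0.865 = 10.4 and 24 × 0.639 = 15.3.
- Power = Φ(ln 2 / √(1/10.4 + 1/15.3) − 0.842) = 81%, against the stated 82%. For a hazard ratio of 0.6 the same formula gives 67%, as stated.

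The stated power is therefore that of a survival comparison of the 36 randomised patients, with no historical controls.

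**2. Inputs for the section 10.3.1 procedure.**

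- Control rate on TKI at 12 months: 50%, from the 12-month median.
- Adaptive rate: 50% under the null; 0.5^(12/24) = 70.7% under the alternative.
- Assumed: 30, 50 or 100 historical patients; a two-sided Fisher preliminary test at 0.10; a pooled Fisher test at one-sided 0.20; one-sided tests at 0.05 in the separate branch.

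All binomial outcomes were enumerated exactly. Where a range is shown for one historical size, the lower figure lets only the randomised-control comparison decide in the separate branch, and the upper figure lets either comparison count.

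**3. How often the preliminary test detects a true gap from 50%** (30 to 100 historical patients):

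| True gap | Detected |
|---|---|
| 10 points | 11-14% |
| 20 points | 30-35% |
| 30 points | 56-67% |

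With 50 historical patients, groups that differ by up to 10 points are pooled in 89-95% of trials.

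**4. False-positive rate of the whole procedure** (both randomised arms truly 50%, 50 historical patients):

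| True historical rate | False-positive rate |
|---|---|
| 60% | 0.05 |
| 50% | 0.15 |
| 48% | 0.18 |
| 46% | 0.21-0.22 |
| 44% | 0.24-0.26 |
| 40% | 0.31-0.34 |

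Across 30 to 100 historical patients the rate is 0.21-0.27 at 44% and 0.26-0.38 at 40%. Fisher's test on the randomised patients alone gives 0.10 whatever the historical group looks like.

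The 40-48% range comes from mixing in unselected patients: 0.8 × 50% + 0.2 × r, where r is the rate on TKI among marker non-responders. The 20% share is the protocol's. The values r = 0, 20% and 40%, giving 40%, 44% and 48%, are assumed.

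If the pooled test is two-sided at 0.10 and only results favouring adaptive therapy are counted, the benchmark is about 0.05. The rates are then 0.05 at 50%, 0.10-0.11 at 44% and 0.14-0.17 at 40%.

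**5. Power at 12 months (70.7% v 50%).**

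- Fisher, randomised patients only: 52%.
- Pooled with 50 historical patients at 50%: 75-77%.
- Pooled with 50 historical patients at 60%: 53%.

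**6. Levels.** The separate branch spends 2 × 0.05 = 0.10. That is a valid Bonferroni split of 0.10, but the design alpha is 0.20.

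**The case against.** The strongest reply is that the inflation rests on assumptions. If the historical patients are comparable, the false-positive rate is about 0.14-0.15 over 30 to 100 patients, below the design level. At 48% with 50 patients it is still 0.18. The highest figures, at 40%, require every marker non-responder to be off treatment by 12 months, although section 4.1 keeps them on conventional therapy. The documents do not say that the historical patients were not marker-selected. Borrowing controls can also be a reasonable trade in a small single-site phase II trial: with 50 comparable patients it lifts Fisher power from 52% to about 75%. On this view it would be enough to specify the group, the test level and the deciding comparison.

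Part of this stands. The size of the inflation is conditional, and it can run in either direction. A Bonferroni adjustment would also normally be read as letting either comparison succeed, so the separate branch is ambiguous rather than empty.

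It does not remove the defect. The plan gives no ground for assuming comparability, and the preliminary test cannot supply one. With 50 historical patients, a shortfall of about 4 points is enough to take the error rate past 0.20. Better specification would help, but the primary result would still rest partly on non-randomised patients admitted by a test that usually misses moderate differences.

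**Conclusion.** The concern holds and should be fixed before the analysis. The firm part needs no assumption: the pooling is compulsory, the group is undefined in the available text (some of which is removed or redacted), and the power statement belongs to a different analysis. The size depends on assumed historical numbers and rates, on independent binomial outcomes, and on a one-sided 0.20 pooled test. With 50 historical patients the false-positive rate runs from 0.05 when their true rate is 60%, through 0.15 at 50%, to 0.31-0.34 at 40%. The same uncertainty can cost power, from about 75% to 53% at a 60% historical rate.

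**What to change.** Delete the test-then-pool step and the two-comparison branch from section 10.3.1. Name one primary test on the randomised arms only: a log-rank test of time to discontinuation at one-sided alpha 0.20, in line with the survival-type comparison powered in sections 10.1 and 10.4. State the censoring time and whether the test is stratified by cancer type, as the randomisation is.

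Any historical comparison should be labelled supportive, with its source and number stated. It should be restricted to patients who meet the trial's eligibility criteria and had the 50% marker drop within two months, and it should use the same time origin as the trial arms.

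The change needs no new patients or data, but it does change the primary test and gives up the apparent precision of borrowed controls. In simulation (20,000 trials) log-rank power is about 81% with 24 to 48 months' follow-up. It is about 76% if everyone is censored at 24 months, which matters because section 6.1.8 says "Any treatment beyond the 24 months specified herein will be considered off protocol". Most of the power comes from using time to event: if the 12-month Fisher test were kept on the randomised patients alone, power would be about 52% and the stated 82% would have to be restated.

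### Section 10.3.1 still tests the adaptive arm against historical controls already flagged as different, so on an either-test reading drift between cohorts can give a false positive

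*Combined protocol and SAP*

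**What the plan says.** Section 10.2 states the hypothesis as a contrast between the two regimens: "We hypothesize that we will prolong time to treatment discontinuation with the adaptive therapy regimen" compared with continuous therapy. Sections 10.1 and 10.4 size the trial for that randomised contrast ("We plan to enroll 24 patients on the adaptive therapy and 12 on the conventional therapy arm") and do not mention historical controls.

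Section 10.3.1 defines the primary measurement as whether a patient is still on TKI 12 months after starting it, tested by Fisher's exact test. It brings in historical controls and begins by comparing them with the trial's own controls. If that comparison gives p>0.1, the two control groups are pooled.

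The other branch opens as follows: "If the historical control patients differ from the control patients of the trial (using a Type I error rate of $p < 0.1").

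In that case, "then they will be compared separately to the experimental group using Fisher Exact test's with a Bonferroni adjusted Type I error rate of $p <" (level: 0.05).

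The section does not say whether one or both of these tests must succeed, or whether 0.05 is the level per test or for the pair. The text available gives no number, source, period, eligibility or 12-month rate for the historical patients.

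**The concern.** Neither group in the pre-test received adaptive therapy. A real difference between them therefore comes from selection, era or care, not from the regimen under study. If the two regimens are equal, the adaptive arm shares whatever separates the trial's patients from the historical ones. The adaptive-versus-historical test then tends to reject for that reason. A stricter threshold does not cure this, because that test's null hypothesis is false even when the regimens are identical.

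Drift in the harmful direction is plausible from the design. Patients are randomised only "when and if the tumor marker drops 50% or more from the baseline level (before initiating TKI treatment) within the first two months of treatment", and nothing applies the same filter to the historical patients. At stake is a positive primary result while the randomised 24 versus 12 comparison shows nothing.

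**Working it through.** **The plan's own power figure.** Inputs from 10.1: 24 and 12 patients, 24 months' uniform accrual, 24 months' minimum follow-up, medians of 24 and 12 months, one-sided alpha 0.20. With exponential times and λ = ln 2/median, the event probability is 1 − (e^(−24λ) − e^(−48λ))/(24λ). This is 0.639 (adaptive) and 0.865 (conventional), or 15.3 + 10.4 = 25.7 events. Power = Φ(ln 2/√(1/15.34 + 1/10.38) − 0.842) = Φ(1.725 − 0.842) = 81%, against the stated 82%. For HR 0.6 the same method gives 67%, as stated. These figures belong to a two-arm survival-type comparison, not to the Fisher procedure of 10.3.1.

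**Inputs for the branch.**
- From the plan: 24 adaptive and 12 conventional patients; a 12-month median, so 50% on TKI at 12 months in both arms if the regimens are equal; pre-test threshold 0.1; test level 0.05.
- Assumed, because not given: historical n of 12 to 100; historical rate from 25% to 70%; two-sided Fisher tests; 0.05 per test (0.025 also shown); either test sufficient.

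**Method.** I enumerated all outcomes of three independent binomials: conventional x of 12, adaptive y of 24, historical z of n. The false-positive probability through this route is the sum of P(x)P(y)P(z) over outcomes where Fisher(x, z) gives p<0.1, and Fisher(y, z) is significant with the adaptive rate higher.

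**Results with 50 historical controls and both arms at 50%:**

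| Historical rate | Branch entered | Win over history given branch | Unconditional, 0.05 per test | Unconditional, 0.025 per test |
|---|---|---|---|---|
| 50% (no drift) | 5.0% | 3.7% | 0.2% | 0.1% |
| 45% | 6.4% | 11.5% | 0.7% | 0.5% |
| 40% | 11.0% | 22.1% | 2.4% | 1.8% |
| 30% | 32.9% | 45.9% | 15.1% | 12.0% |
| 25% | 47.6% | 59.6% | 28.3% | 23.4% |
| 70% (history better) | 32.9% | about 0 | about 0 | about 0 |

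The unconditional column is the product of the two before it, for example 0.329 × 0.459 = 0.151. Only wins favouring adaptive are counted, so the nominal level of the two-sided 0.05 test in that direction is 2.5%.

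**Historical sample size.** At a 40% historical rate, n = 12, 24, 50 and 100 give 2.2%, 2.2%, 2.4% and 2.1%. At 30% they give 7.5%, 9.8%, 15.1% and 16.9%.

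**Role of the randomised test.** In the 30% row, the randomised comparison favours adaptive in 0.07% of trials through this branch, so almost every win there is over history alone. If both tests had to succeed, the branch would give under 0.05% in every row of the table.

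**How much drift the plan itself supports.** Section 10.1 expects 20% of patients not to qualify for randomisation. If those patients had a 12-month rate r between 0 and 50%, an unselected cohort would have 0.8 × 0.50 + 0.2 × r = 40% to 50%. Selection alone therefore gives 0 to 10 points of drift.

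**The case against.** A reader might infer that the plan allows success to be claimed on the historical test alone. It does not say so. The either-test rule is inferred from the word Bonferroni, since requiring both tests would need no adjustment. That inference is reasonable, but part of the defect is simply a missing success rule.

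A reader might also take the false-positive risk to be tens of per cent. The 22% to 60% figures are conditional on entering the branch and rest on an assumed historical cohort. The only selection figure in the plan supports at most about 10 points of drift, and so about 2%. Differences in era or care could add to that, but nothing in the documents quantifies them. Against the one-sided 0.20 that the design accepts, this branch alone exceeds 20% only in the 25-point row of the table.

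Nor does the pre-test prove that the cohorts differ: with 12 trial controls and 50 historical ones, chance alone opens the branch in 5% of trials. The direction is also uncertain. Section 5.1 admits patients with other prior TKIs and ECOG status up to 2, who could do worse than an undefined historical cohort, and the inflation would then vanish.

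These points limit the size and certainty of the effect. They do not justify keeping a flagged, non-randomised group as one of two primary comparisons with no rule for which one decides.

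**Conclusion.** The point holds in a limited form. In the p<0.1 branch, the primary analysis retains a control group that its own pre-test has flagged. If either test can carry the claim, drift can produce a positive result with equal regimens. With 50 historical controls at 0.05 per test, the unconditional risk is about 0.2% with no drift, 0.7% at 5 points, 2.4% at 10, 15% at 20 and 28% at 25. At 0.025 per test it is about 1.8%, 12% and 23% at 10, 20 and 25 points. It is about 0 if historical patients do clearly better, and negligible if both tests must succeed.

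These figures rest on an assumed historical size and rate, a 50% rate in both randomised arms, and an inferred success rule. The plan's own selection supports only the lower end of the range. This should be fixed because it sits in the primary analysis and is cheap to remove; the documents do not show that large inflation is likely.

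**What to change.** Replace the last bullet of 10.3.1 with: *If the historical controls differ from the trial's conventional arm (p<0.1), the primary conclusion rests only on the randomised adaptive versus conventional comparison, tested once without a Bonferroni split at the one-sided alpha of 0.20 used in 10.1 and 10.4. The adaptive versus historical contrast is descriptive (rates with 95% CI) and cannot support a claim of efficacy.*

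If the sponsor intends another level, 10.1, 10.3.1 and 10.4 must state the same one. With a one-sided 0.20 Fisher test of 24 versus 12 and both arms at 50%, the randomised comparison has a 10.4% false-positive probability overall. That caps what this branch can contribute, whatever the historical cohort looks like.

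The change needs no patients or data. Its cost is the loss of the historical comparison as a second route to a positive result. It does not address drift that enters when the groups are pooled at p>0.1, which is a separate issue and needs its own decision.

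### The separate-comparison threshold in 10.3.1 (Bonferroni p < 0.05, a split of 0.10) does not agree with the one-sided alpha of 0.20 on which the stated power rests

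*Combined protocol and SAP*

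**What the plan says.** Section 10.1 plans the trial at "one-sided $\alpha = 0.20", and 10.4 repeats this. Section 10.2 states: "The power of the study to detect this difference is 82% for an alpha of 0.20". No other level is given for the adaptive-versus-conventional comparison of the primary endpoint. The power statement belongs to a time-to-event comparison ("which is a 'survival analysis'-type statistical comparison") of 24 adaptive and 12 conventional patients.

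Section 10.3.1 analyses the primary endpoint with Fisher's exact test on treatment status at 12 months. It first compares historical with trial controls at a level of 0.1. If they do not differ, they are pooled. If they differ, each is compared separately with the adaptive arm "with a Bonferroni adjusted Type I error rate of $p < 0.05". The section does not give the level before adjustment, the side of the Fisher tests, or any level for the pooled comparison.

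**The concern.** A Bonferroni adjustment divides a family level by the number of tests. Two tests at 0.05 imply a family level of 0.10. In 10.3.1 the value 0.1 is used only to decide whether the control groups may be pooled, which is a different hypothesis. The design level of 0.20 would give 0.10 per test.

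This threshold decides whether the primary result is positive when the controls are not pooled. In that case the randomised comparison is held to a level four times stricter than the design level, or stricter still if p is read as two-sided. A result that meets the design criterion could then be declared negative, with nothing in the plan explaining the difference.

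**Working it through.** **1. Which alpha lies behind the 82%.** Inputs from 10.1: "We plan to enroll 24 patients on the adaptive therapy and 12 on the conventional therapy arm"; medians of 12 and 24 months; uniform accrual over 24 months; minimum follow-up of 24 months. With exponential times and hazard λ = ln 2 / median, the event probability is 1 − (e^(−24λ) − e^(−48λ)) / (24λ).

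- Conventional: 1 − (0.25 − 0.0625)/1.386 = 0.865; × 12 = 10.38 events.
- Adaptive: 1 − (0.50 − 0.25)/0.693 = 0.639; × 24 = 15.34 events.
- SE of log HR = √(1/15.34 + 1/10.38) = 0.402.
- Power at one-sided 0.20 = Φ(0.693/0.402 − 0.842) = 81%, against the stated 82%.
- At HR 0.60 the same method gives 67.5%, against the stated 67%.
- Simulated log-rank power is 81.3% and 67.5%.
- Reading the 0.20 as two-sided gives only 65% to 70% at HR 0.50.

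The stated power therefore rests on a one-sided 0.20.

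**2. The split over two tests.**

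| Family level | Per test |
|---|---|
| 0.20 | 0.10 |
| 0.10 | 0.05 |
| 0.05 | 0.025 |

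Two tests at 0.05 total at most 0.05 + 0.05 = 0.10, below 0.20. The split itself cannot inflate type I error.

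**3. Cost in power for the randomised comparison.** The 12-month on-treatment rates under the design medians are 2^(−12/12) = 0.50, 2^(−12/24) = 0.707 (HR 0.50) and 2^(−12/20) = 0.660 (HR 0.60). Power is the sum of the binomial probabilities of all 25 × 13 outcomes of 24 versus 12 patients whose Fisher p falls below the threshold.

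| Threshold | Power, HR 0.50 | Power, HR 0.60 | Size, common rate 0.4–0.7 |
|---|---|---|---|
| one-sided 0.20 | 52% | 40% | 10–12% |
| one-sided 0.10 | 36% | 26% | 5–6% |
| one-sided 0.05 | 22% | 14% | about 2% |
| two-sided 0.05 | 15% | 9% | 1–2% |

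These are unconditional figures: they ignore that the branch is reached only after the control groups differ.

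**4. Can it change the result?** Suppose 6 of 12 trial controls are still on treatment at 12 months. Success then needs 17 of 24 adaptive patients at one-sided 0.20, 19 at 0.10, 20 at 0.05 and 21 at two-sided 0.05.

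**5. Within the branch.** The documents give neither the number nor the rate of the historical controls. Assume 20, 50 or 100 of them, the same true rate as the trial controls, and a two-sided Fisher pre-test at 0.1. The branch is then entered about 5% to 7% of the time. Given entry, for the one-sided randomised test:

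| Threshold | Size, common rate 0.5 or 0.6 | Power, 0.707 vs 0.50 |
|---|---|---|
| 0.05 | 12–17% | 41–46% |
| 0.10 | 23–32% | 47–49% |
| 0.20 | 29–38% | 50% |

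The raised size comes from the pre-test, which selects extreme trial-control results; it does not come from the split. If the true control rates differ strongly, entry is common and the results move towards those in step 3.

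**The case against.** The strongest reply is that 10.3.1 contains no arithmetic mistake. It never says that 0.05 was derived from 0.20, and 0.05 is a valid Bonferroni level for two tests in a family of 0.10. The 0.20 is attached to a time-to-event comparison, whereas these are Fisher tests, one of them against non-randomised patients, where a stricter level could be deliberate. A reader might infer that 0.05 is simply wrong and 0.10 is the correct value. The documents do not support that, because the family level and the side of the Fisher tests are unstated. One-sided 0.10 follows only if the one-sided 0.20 governs them.

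What remains is the inconsistency. Sections 10.1, 10.3.1 and 10.4 all concern the same primary endpoint. If 0.20 governs, the threshold does not match it. If a family level of 0.10 was meant, it is stated nowhere for this comparison and the 82% does not apply to it.

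Two further points stand. First, the step 3 losses are unconditional; if the control groups differ only by chance, the power lost within the branch is a few points. Second, a reader might take a looser threshold to be safely inside the accepted 0.20. That holds unconditionally, but not within the branch under the step 5 assumptions.

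It is also fair to say that a larger mismatch sits beside this one: the powered analysis is time-to-event, while the planned one is a 12-month Fisher test with about 52% power even at one-sided 0.20. That is a separate matter. While this branch stands, resolving it would not by itself explain the threshold.

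**Conclusion.** The concern holds as an inconsistency between 10.3.1 and the design alpha in 10.1, 10.2 and 10.4. The per-test 0.05 implies a family level of 0.10 with no stated side; the design level is 0.20, one-sided in 10.1 and 10.4. The effect is conservative: for the randomised comparison at HR 0.50, unconditional power is 22% at one-sided 0.05 (15% if two-sided), against 36% at 0.10 and 52% at 0.20. This assumes exponential times, the design medians, full 12-month status for all 36 randomised patients and no allowance for entry into the branch. Behaviour within the branch cannot be fixed from the documents. They support neither a claim of inflated type I error from the split nor a claim that 0.10 was the intended threshold.

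**What to change.** Make the threshold in 10.3.1 agree with the design alpha, before outcome data are seen.

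- **Preferred:** in this branch, test adaptive against the randomised controls alone at one-sided 0.20, and report the comparison with the differing historical controls descriptively. With one confirmatory test no split is needed.
- **If both tests are kept under a 0.20 family level:** use one-sided 0.10 for each and show the division.
- **If a family level of 0.10 was intended:** state it with its side and restate the power. For the time-to-event calculation in step 1, power at HR 0.50 falls from 81% to 67% at one-sided 0.10, or to 53% if the 0.10 is two-sided.

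In every case, state the same alpha and side for the pooled-control branch.

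The edit is a few lines. The price is a higher per-test false-positive rate than at one-sided 0.05: unconditionally about 10% to 12% at one-sided 0.20, or 5% to 6% at 0.10, against about 2%. Within the branch it is higher when the control groups differ only by chance (step 5), and the plan should acknowledge this.
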